11.2 Evaluation of Dabrafenib + GSK2141795 (D+G)

a. Analysis of Phase I Portion

Section 7.3 provides the details of the study design for the Phase I Portion of the study. The Phase I Portion will be a limited dose-escalation.

The primary objective of the Phase I Portion will be to determine the maximum tolerated dose (MTD) of GSK2141795 and dabrafenib in patients with BRAF mutant locally advanced or metastatic cancer. The regimen will be considered safe and the MTD determined if the dose-limiting toxicity rate is ≤ 33%.

Prior to implementation of the Phase II Portion, a temporary closure will occur in order to assess dose and to evaluate the safety profile more fully.

b. Analysis of Phase II Portion

Note: Effective November 15, 2014, this trial will not proceed to the Phase II study of dabrafenib and GSK2141795, but will be moving to an evaluation of triple therapy.

The study will be conducted in two sequential parts. Patients enrolled to the Phase I Portion will not be included in the analysis of the Phase II Portion.

The primary objective of the Phase II Portion of this study is to evaluate the objective response rate (confirmed and unconfirmed, complete and partial responses) of GSK2141795 used in combination with dabrafenib in patients with Stage IV or unresectable Stage III melanoma who have acquired resistance to BRAF inhibitor-based therapy. Resistance to BRAF inhibitor-based therapy will be defined as progressive disease by RECIST 1.1 criteria while receiving therapy with a BRAF inhibitor (vemurafenib or dabrafenib, alone or in combination with a MEK inhibitor). This may be innate resistance (patients who never achieved a tumor response while on BRAF inhibitor therapy) or acquired resistance (progression after having a tumor response to BRAF inhibitor therapy).

It is assumed that this regimen will not be of further interest if the true response rate is less than 5% (null) and that a true response rate of 25% or more would be of considerable interest for further investigation (alternative).

Parallel patient enrollment will be implemented for two strata (prior therapy with BRAF-inhibitor only versus prior therapy with both a BRAF-inhibitor and a MEK-inhibitor), and a two-stage design will proceed separately for each stratum as follows: In the first step, 9 eligible patients will be accrued. If necessary, the study may be temporarily closed while response data matures. If zero responses are observed, the study will be closed with the conclusion that this regimen does not warrant further study. If at least one response is observed, an additional 15 eligible patients will be accrued. Three or more responses out of 24 will be considered evidence that this regimen warrants further study, provided other factors such as overall survival and adverse events also appear favorable. This design has 90% power with a one-sided alpha of 10%.

11.3 Evaluation of Dabrafenib + Trametinib + GSK2141795 (D+T+G)

a Analysis of Phase I Portion

Section 7.4 provides the details of the study design for the Phase I Portion of the study. The Phase I Portion will be a limited dose-escalation.

The primary objective of the Phase I Portion will be to determine the maximum tolerated dose (MTD) of GSK2141795, dabrafenib and trametinib in patients with BRAF mutant locally advanced or metastatic cancer. The regimen will be considered safe and the MTD determined if the dose-limiting toxicity rate is \leq 33%.

Prior to implementation of the Phase II Portion, a temporary closure will occur in order to assess dose and to evaluate the safety profile more fully.

b Analysis of Phase II Portion

The study will be conducted in two sequential parts. Patients enrolled to the Phase I Portion will not be included in the analysis of the Phase II Portion.

The primary objective of this portion study is to evaluate the objective response rate (confirmed and unconfirmed, complete and partial responses) of GSK2141795 used in combination with dabrafenib and trametinib in patients with Stage IV or unresectable Stage III melanoma who have acquired resistance to BRAF inhibitor-based therapy. Resistance to BRAF inhibitor-based therapy will be defined as progressive disease by RECIST 1.1 criteria while receiving therapy with a BRAF inhibitor (vemurafenib or dabrafenib, alone or in combination with a MEK inhibitor). This may be innate resistance (patients who never achieved a tumor response while on BRAF inhibitor therapy) or acquired resistance (progression after having a tumor response to BRAF inhibitor therapy).

It is assumed that this regimen will not be of further interest if the true response rate is less than 15% (null) and that a true response rate of 35% or more would be of considerable interest for further investigation (alternative).

A two-stage design will be used for patient accrual. In the first step, 10 eligible patients will be accrued. If necessary, the study may be temporarily closed while response data matures. If 0-1 responses are observed, the study will be closed with the conclusion that this regimen does not warrant further study in the Group A population. If at least 2 responses are observed, an additional 23 eligible patients will be accrued. Eight or more responses out of 33 will be considered evidence that this regimen warrants further study, provided other factors such as overall survival and adverse events also appear favorable. This design has 87% power with a one-sided alpha of 0.9%.

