Despite the improved PFS with dabrafenib and trametinib in the first line compared with dabrafenib alone, the addition of the MEK inhibitor trametinib alone to the BRAF inhibitor dabrafenib after disease progression on dabrafenib alone vields only modest clinical benefits with an objective response rate of only 9-15% and a median progression-free survival of only 3.6 months. (27) As a result, the combination of dabrafenib and trametinib after disease progression on a BRAF inhibitor has not been FDA approved and the vast majority of BRAF mutant melanoma patients treated with BRAF inhibitor monotherapy have no effective targeted therapy options after disease progression on these agents (median PFS 5-6 months). (3,4) The current study will examine the safety and efficacy of combined BRAF, MEK, and AKT inhibition based on preclinical data suggesting that resistance to MAPK inhibitors may be mediated by activating PI3K pathway mutations and non-mutational activation of the PI3K pathway. (12,16,19-25) Phase II testing of this combination in treatment naïve patients is based on data suggesting that 1. PI3K activity may be essential for the survival of senescent cells after maximal tumor killing from dabrafenib and trametinib and 2. The molecular evolution of surviving tumors in patients with disease progression on BRAF inhibitors may make the addition of additional oncogenic pathway inhibitors less effective at the time of progression than at the time of the initiation of BRAF inhibitor therapy ([name], unpublished data).

The rationales for the **S1221** treatment arms are summarized below:

Treatment arm	Prior treatment	Rationale
D + G Phase I (BRAF ^{V600X} solid tumors)	Any	Identify MTD.
D + T + G Phase I (BRAF ^{V600X} melanoma)	Any	Identify MTD, Early response signal.
D + T + G Phase II	Prior PD on BRAFi or BRAFi + MEKi	Allows early assessment of benefit (ORR). Clinical need: Addition of MEKi alone after progression on BRAFi only modestly beneficial.
(BRAF ^{V600X} melanoma)	No prior BRAFi or MEKi	Preclinical data suggests potential for more durable benefit due to targeting of senescent cells and prevention of emergence of resistance due to PI3K pathway activation.

Study outline

Dabrafenib + GSK2141795:

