Phase I dose escalation will be performed according to a standard 3+3 scheme to identify the maximum tolerated dose (MTD) of dabrafenib with GSK795 prior to Phase 1 testing of dabrafenib, trametinib, and GSK2141795. The dabrafenib + GSK795 combination without trametinib will not continue to Phase 2 testing under the current protocol.

Dabrafenib + Trametinib + GSK2141795:

3 + 3 dose escalation will be performed to identify the MTD of dabrafenib, trametinib, and GSK2141795 in combination. Phase II testing will then be performed to obtain additional safety information and preliminary efficacy data in two populations: 1. Patients with prior disease progression on a BRAF inhibitor alone or a BRAF + MEK inhibitor combination and 2. Patients with no prior exposure to BRAF or MEK inhibitors.

Hypothesis

- The AKT inhibitor GSK795 can be combined safely with the BRAF inhibitor dabrafenib and the MEK inhibitor trametinib.
- In patients with prior disease progression on BRAFi monotherapy or a BRAFi + MEKi combination, the addition of GSK795 and trametinib to dabrafenib will increase the overall response rate compared with historical controls treated with standard of care chemotherapy.
- Triple therapy with dabrafenib, trametinib, and GSK795 will increase the overall response rate in BRAFi/MEKi naïve patients compared with historical controls treated with dabrafenib and trametinib without a PI3K pathway inhibitor.

Inclusion of Women and Minorities

This study was designed to include women and minorities, but was not designed to measure differences of intervention effects. The anticipated accrual in the ethnicity/race and sex categories is shown in the table below.

Ethnic Category			
	Females	Males	Total
Hispanic or Latino	2	1	3
Not Hispanic or Latino	32	62	94
Total Ethnic	34	63	97
Racial Category			
American Indian or Alaskan Native	2	0	2
Asian	0	0	0
Black or African American	0	0	0
Native Hawaiian or other Pacific Islander	0	0	0
White	32	63	95
Racial Category: Total of all Subjects	34	63	97

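### Does the triple-therapy Phase II need a planned response rate by prior MEK-inhibitor exposure?

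*Combined protocol and SAP*

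**What the plan says.** Section 1.2 sets the Phase II objective as the response rate in BRAF-mutant melanoma after progression on a BRAF inhibitor or on a BRAF plus MEK inhibitor combination. Section 2.0 uses the same group. The rationale table describes it as "Prior PD on BRAFi or BRAFi + MEKi". The hypothesis opens "In patients with prior disease progression on BRAFi monotherapy or a BRAFi + MEKi combination" and names one comparator, "historical controls treated with standard of care chemotherapy".

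Section 11.3b turns this into a single test: "It is assumed that this regimen will not be of further interest if the true response rate is less than 15% (null"), with 35% as the alternative. Ten patients enter first, and the trial stops at 0 or 1 responses. Otherwise 23 more enter. At the end, "Eight or more responses out of 33 will be considered evidence that this regimen warrants further study". The same sentence then attaches a condition to that conclusion: "provided other factors such as overall survival and adverse events also appear favorable".

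Section 5.2b permits prior trametinib without a quota, and Section 6.0 has no stratification factors. Section 11.4 adds survival, progression-free survival, toxicity and dose-delivery summaries. Section 11.5 relates response to translational markers only. Prior MEK-inhibitor exposure divides patients only in the D+G Phase II design of Section 11.2b, which did not go forward.

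**The concern.** The two prior-therapy groups are not alike in what the regimen offers them. For a patient who has had only a BRAF inhibitor, both trametinib and GSK2141795 are new classes. For a patient who has failed the BRAF plus MEK combination, only the AKT inhibitor is new. The rationale table argues from the first setting: "Clinical need: Addition of MEKi alone after progression on BRAFi only modestly beneficial". The only benchmark given for adding trametinib after progression, "an objective response rate of only 9-15% and a median progression-free survival of only 3.6 months", also comes from patients who progressed on dabrafenib alone. Its upper end equals the 15% null. No rate is given for patients who failed the combination. The abandoned D+G design had used this same factor to form two strata.

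A reader could therefore fear that a pooled pass is driven by BRAF-inhibitor-only patients and then read as activity in everyone. The planned outputs would look the same either way. At stake would be the population carried into a next study.

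**Working it through.** **1. The plan's own figure.** Inputs from Section 11.3b: n1 = 10, continue if X1 ≥ 2; n2 = 23, pass if X1 + X2 ≥ 8.

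P(pass | p) = Σ over x = 2..10 of P(X1 = x | 10, p) × P(X2 ≥ max(0, 8 − x) | 23, p)

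- At p = 0.35 this gives 0.872, so the stated 87% is confirmed.
- At p = 0.15 it gives 0.092. The printed one-sided alpha of 0.9% does not match this. That is a separate matter, and nothing below depends on it.

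**2. What a minimum pass could contain.** 8/33 is 24%, exact (Clopper-Pearson) 95% CI 11–42%. The documents give no case mix, so a 17/16 split is assumed for illustration:

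| Responses | Group of 17 | Group of 16 |
|---|---|---|
| 4 + 4 | 24% (7–50%) | 25% (7–52%) |
| 6 + 2 | 35% (14–62%) | 13% (2–38%) |
| 8 + 0 | 47% (23–72%) | 0% (0–21%) |

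The fear is arithmetically possible: all three rows pass.

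**3. What the table could establish.** If both groups share one rate, then given 8 responses the number falling in the 17 is hypergeometric.

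- P(8 in the 17) = C(17,8)/C(33,8) = 24,310/13,884,156 = 0.0018.
- P(6 or more in the 17) = (1,485,120 + 311,168 + 24,310)/13,884,156 = 0.131.

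Only the extreme row would be informative. For 6/17 against 2/16 the two-sided Fisher p is 0.22, and the intervals overlap from 14% to 38%. If the true rates were 35% and 15%, a 17/16 comparison would reach p<0.05 about 18% of the time. After a stage 1 stop with, say, 5 and 5 patients, 1/5 gives 1–72% and 0/5 gives 0–52%.

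**4. How often one group could carry the pooled rule.** Assume the combination-failure group has a true rate of 5%, and treat each patient as drawn at the pooled rate.

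- Even split, other group at 35%: pooled 0.5 × 35% + 0.5 × 5% = 20%, P(pass) = 0.28.
- Even split, other group at 50%: pooled 27.5%, P(pass) = 0.64.
- 75% BRAF-inhibitor-only at 35%: pooled 0.75 × 35% + 0.25 × 5% = 27.5%, P(pass) = 0.64.
- 25% BRAF-inhibitor-only at 35%: pooled 12.5%, P(pass) = 0.04.

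The answer depends on a case mix and on group rates that the documents do not give. In each case the rule still does what it was set up to do, which is to judge the pooled rate.

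**5. Does any conclusion go wrong if the plan is followed as written?** Sections 1.2, 2.0 and 11.3b all define the same combined population. A pass supports further study in that population. No text claims activity separately in patients who failed the combination.

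**The case for a change.** The strongest case for the concern is that the factor was already known. It had defined strata in the D+G design, the groups differ in the number of new drug classes they receive, and naming the breakdown in advance would spare it any suspicion of selection afterwards. An 8-to-0 pattern would be worth seeing, and the cost is one sentence and one table.

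Part of this stands. The breakdown is absent from the plan, and showing it at reporting would be sensible. Three things keep this from being a defect.

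- The D+G strata belonged to a different regimen with a 5% null and a separate two-stage design in each stratum. They do not make later pooling wrong.
- Prespecification protects tests and claims, and this table would carry neither. Section 11.3b does not forbid it, and its closing proviso on other factors is open-ended.
- Using the table to narrow the population to which the result applies would ask more of it than the figures above can bear.

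The suggested variable also fits imperfectly. Section 5.2b permits prior trametinib without saying when it was given or whether the patient progressed on it, so exposure is not the same as failure of the combination. Section 11.3b also pools innate and acquired resistance, another plausible source of mixed response, so singling out one factor is a matter of preference.

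**Conclusion.** The concern does not hold. Pooling is a consistent, stated choice, the 8-of-33 rule is valid for the population it names, and its power at 35% is 0.872 as claimed. The missing breakdown would alter no decision rule, sample size or error rate. At about 16 or 17 patients per group it could expose only extreme imbalance: 0.2% probability under a common rate for 8–0, but 13% for 6–2 or more lopsided.

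This rests on two assumptions. The by-group figures use an illustrative 17/16 split, because the documents state no case mix. The view that the table can be produced at reporting assumes that prior MEK-inhibitor treatment is recorded at baseline; the form fields are not in the documents, so that cannot be checked. Neither assumption affects the validity of the pooled result.

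### The Phase II three-drug design (D+T+G) states a one-sided alpha of 0.9%, but its own decision rule has an alpha of about 9.2%

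*Combined protocol and SAP*

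**What the plan says.** Section 11.3b fixes every element of the Phase II rule for the three-drug combination.

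- Null: "this regimen will not be of further interest if the true response rate is less than 15% (null").
- Alternative: "a true response rate of 35% or more would be of considerable interest for further investigation (alternative").
- First stage: "In the first step, 10 eligible patients will be accrued". "If 0-1 responses are observed, the study will be closed".
- Second stage: "If at least 2 responses are observed, an additional 23 eligible patients will be accrued".
- Success: "Eight or more responses out of 33 will be considered evidence that this regimen warrants further study", subject to survival and adverse events also looking favourable.
- Error rates: "This design has 87% power with a one-sided alpha of 0.9" per cent.

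Section 11.2b describes the companion two-drug design (D+G), which was dropped before Phase II. There the statement is "This design has 90% power with a one-sided alpha of 10" per cent.

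**The concern.** A bar of 8 responses in 33 is an observed rate of 24%, only nine percentage points above the 15% null. With so few patients that cannot be a test at the 1% level. It also cannot sit beside 87% power against 35% with this sample size.

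The figure matters because it is the only type I error rate given for the primary Phase II endpoint, and this is the only Phase II design still active. The trial is single-arm, so the rule and its stated error rates are the formal basis for deciding whether to take the combination further. A reader who trusts the sentence would believe that a regimen with a true 15% response rate passes about once in 111 trials (1/0.009). A publication could repeat the figure.

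**Working it through.** **Inputs** (all from Section 11.3b): n1 = 10; stop at 0 or 1 responses; n2 = 23; success at 8 or more of 33; p0 = 0.15; p1 = 0.35.

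**Formula.** Let X1 be Bin(10, p) and X2 be Bin(23, p), independent. Success requires X1 ≥ 2 and X1 + X2 ≥ 8:

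P(success | p) = Σ over x = 2,…,10 of P(X1 = x) × P(X2 ≥ 8 − x).

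**Step 1: the plan's power (p = 0.35).**

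| x in stage 1 | P(X1 = x) | P(X2 ≥ 8 − x) | Product |
|---|---|---|---|
| 2 | 0.1757 | 0.8691 | 0.1527 |
| 3 | 0.2522 | 0.9449 | 0.2383 |
| 4 | 0.2377 | 0.9819 | 0.2334 |
| 5 | 0.1536 | 0.9957 | 0.1529 |
| 6 | 0.0689 | 0.9993 | 0.0689 |
| 7 to 10 | 0.0260 | about 1 | 0.0260 |
| **Sum** | | | **0.8721** |

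This matches the stated 87%, so the rule has been read as its authors meant it.

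**Step 2: the plan's alpha (p = 0.15).**

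| x in stage 1 | P(X1 = x) | P(X2 ≥ 8 − x) | Product |
|---|---|---|---|
| 2 | 0.2759 | 0.1189 | 0.0328 |
| 3 | 0.1298 | 0.2560 | 0.0332 |
| 4 | 0.0401 | 0.4604 | 0.0185 |
| 5 | 0.0085 | 0.6920 | 0.0059 |
| 6 | 0.0013 | 0.8796 | 0.0011 |
| 7 to 10 | 0.0001 | about 0.98 | 0.0001 |
| **Sum** | | | **0.0916** |

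The result is 9.16% against a stated 0.9%, a ratio of 0.0916/0.009 = 10.2. A simulation of 2,000,000 trials also gave 9.16%. The chance of stopping after the first stage is 54.4% at a true rate of 15% and 8.6% at 35%.

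**Step 3: could another cut-off give both figures?** Stage sizes and first-stage rule unchanged:

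| Responses needed of 33 | Alpha at 15% | Power at 35% |
|---|---|---|
| 8 (plan) | 9.2% | 87.2% |
| 9 | 4.3% | 82.0% |
| 10 | 1.8% | 73.7% |
| 11 | 0.64% | 62.2% |

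No row has an alpha near 0.9% together with 87% power.

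**Step 4: other readings of the 8-of-33 rule at a 15% null.**

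- Single stage, no interim look: 11.1%.
- Normal approximation: 6.9% without continuity correction, 10.7% with it.
- First stage passed with 1 response: 10.8%. With 3 responses: 5.9%.
- The null rate at which the plan's rule has alpha 0.9%: about 9.6%, not 15%.

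**Step 5: the method checked on Section 11.2b.** That design enrols 9, continues with at least 1 response, adds 15, and succeeds at 3 or more of 24, with rates of 5% and 25%. The same formula gives alpha 9.3% and power 90.3%, against 10% and 90% stated. The protocol's other two-stage design therefore agrees with the exact calculation to within rounding.

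**The case against.** Nothing found rescues the 0.9%. The sentence is intact running text, no other section gives an alpha for this design, and no multiplicity rule is stated that would lower it. The survival and safety proviso could make the real go-rate lower. It has no numerical criterion, though, and anything that lowered the go-rate would lower power too, so it cannot explain 0.9% beside 87%.

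Three qualifications do stand.

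- **The 9.2% is a maximum.** The null covers all rates below 15%, and 9.2% applies at the boundary. The same rule passes a regimen 3.8% of the time at a true rate of 12.5%, 1.1% at 10% and 0.01% at 5%. The accurate statement is about 1 in 11 at a true rate of 15%, before the unquantified proviso.
- **The confidence interval is only an illustration.** The ordinary exact 95% interval for 8/33 is 11% to 42% and includes 15%. It puts 2.5% in each tail and ignores the interim look. Any cut-off with a one-sided alpha near 9% would be expected to behave this way, so it is not a second fault.
- **The cause is inferred.** The documents do not say which figure was intended.

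It can also be said that the go/no-go rule is expressed in response counts, so conduct is unaffected. That is true. It limits the consequence to how the result is interpreted and reported.

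**Conclusion.** The stated alpha is wrong for the stated rule. The exact one-sided alpha is 9.2% at a true response rate of 15%, about ten times the printed 0.9%. The stated 87% power is right.

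The result assumes only independent responses with a common probability, the full 10 and 33 eligible patients, and the cut-offs as printed. The proviso on survival and adverse events is left out because it cannot be quantified. A misplaced decimal is the likeliest cause: power, stage sizes and cut-offs all fit 9%, and the companion design worked to 10%.

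The design itself is not unsound. An alpha near 9% is consistent with the protocol's other Phase II design. Because the error concerns the false-positive rate of the primary endpoint and runs in the favourable direction, it has to be corrected.

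**What to change.** In Section 11.3b, have the study statistician confirm the intended error rate, then change the one-sided alpha from 0.9% to 9% (exact 9.2%). Stage sizes, cut-offs and the 87% power stay as printed, and no further patients are needed. Any report of the trial should use the corrected value.

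The cost is one figure in the protocol, and the stated type I error becomes less favourable. If 0.9% was really intended, a text edit is not enough. With the present stage sizes and first-stage rule the bar would rise to 11 of 33, power would fall to 62%, and the design would have to be reworked to keep 87%.
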